**DATA COLLECTION:** Data collection will include daily weekday virtual FCR observations; parent surveys; and review of the EHR, incident reports, and helpdesk technical issues log. Outcomes (for Aims 1-3) will include the following: FCR parent attendance proportion (captured using weekday rounding observations), length of stay (captured using EHR data), breast milk feeding initiation and breast milk feeding at discharge (captured using EHR data) and at 90 days after discharge (captures via parent via parent/guardian survey), growth failure and growth velocity (captured using EHR data), time to first social work contact (captured using EHR data), temperature instability (captured from an existy NICU quality dataset), feeding difficulty (captured from an existy NICU quality dataset), central line-associated bloodstream infection (captured from an existy NICU quality dataset), central line days (captured from an existy NICU quality dataset), antibiotics days (captured from an existy NICU quality dataset), medical errors (captured using data from EHR, incident reporting system, and solicited reports), 30-day revisit and readmission (captured via EHR and survey) parent experience and family-centered care (captured via parent/guardian survey at discharge), parent activation (captured via parent/guardian survey at discharge), parent distress: depression and anxiety (captured via parent/guardian survey at 0, 30, 60, 90 days from discharge), parent sleep (captured via parent/guardian survey at 0, 30, 60, 90 days from discharge), and parent quality of life (captured via parent/guardian survey at 0, 30, 60, 90 days from discharge).

RE-AIM (Aim 3) implementation evaluation data collection will include the

**PROTOCOL TITLE: Virtual Family-Centered Rounds in the Neonatal Intensive Care Unit:  
A Randomized Clinical Trial**

following: subscribed vs. not subscribed parents among intervention-arm parents, heterogeneity of intervention effects (interactions between neonate/parent characteristics and the intervention effect), virtual FCR attempts with technical issues (sounds, video, other), trial-related 24/7 helpdesk line calls, ExtendedCare wait time when parent(s) join, ExtendedCare connection time, device model (e.g., iPhone, Android, etc.) that parent uses to connect to the ExtendedCare visit, interruptions requiring a break in rounds due to a delivery or new admission, and virtual FCR use with NICU parents post-trial (maintenance).

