**8) Data and/or Specimen Management and Confidentiality**

I understand that if this study involves the use of the UC Davis Health Electronic Health Record (EMR/EPIC) also contains the clinical data for Marshall Medical Center (MMC). I understand that MMC patient data cannot be accessed for research purposes and that I must take the necessary steps to ensure that MMC data is not accessed, used, or disclosed for UC Davis Health research purposes.

I understand that if this study involves use of UC Davis students' educational records (including records in the PI's own possession such as course exams/assignments), I must consult with the Registrar's office to see if all requirements of the Family Educational Rights and Privacy Act (FERPA) are satisfied.

**DATA ANALYSIS:** We will analyze subject data according to their assigned group (intervention vs. control). We will use descriptive statistics to summarize subject-level characteristics. We will compare neonatal and parental characteristics between study arms using Pearson's Chi-square test for categorical variables, t-test for normally distributed continuous variables, and nonparametric equality-of-medians test for non-normally distributed continuous variables. Generalized linear models will be used to estimate effect sizes and to test hypotheses for study outcomes, using a binary indicator for intervention assignment as the independent variable of interest and including a parsimonious set of demographic and clinical characteristics as covariates. We will analyze all available data and anticipate high data completion rates, based on our pilot trial. We will conduct sensitivity analyses using multiple imputation approaches for missing data to complement the primary analysis.

**SAMPLE SIZE:** We specified effect sizes of interest for all the trial outcomes and determined the necessary sample size to satisfy each. The sample size estimation that satisfies length of stay requirements also satisfies requirements for all other outcomes of interest, except for medical errors (which are rare and

**PROTOCOL TITLE: Virtual Family-Centered Rounds in the Neonatal Intensive Care Unit:  
A Randomized Clinical Trial**

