thus this outcome will be considered exploratory. Outcome distributional assumptions were based on data from our pilot trial or other relevant literature. Pilot trial baseline mean log transformed length of stay +/- standard deviation (SD) was 3.0 +/- 1.0 days. Minimally clinically important differences (MCID) were based on the literature when available or via consensus opinion elicited from NICU clinicians we consulted. For the length of stay outcome, experts specified that a 25% reduction in geometric mean length of stay was of interest. A randomized sample of 447 neonates (298 intervention, 149 control) subject to 4% attrition in each arm yields a sufficient sample size (429 neonates) to provide 80% power (under two-sided testing, alpha=5%) to detect this MCID. This estimated attrition is based on 4 of 110 randomized subjects in the pilot trial being excluded from final analysis (e.g., child protective visitation restrictions placed after randomization). Parent-reported outcomes assume a survey response rate of 75% (thus n=321 parents). Note: Regarding sample size for the interviews, we anticipate interviewing ~15 parents, ~10 nurses, and ~10 physicians. Consistent with standard qualitative methods, we will continue to sample interview participants until we reach thematic saturation, thus we cannot specify a priori the exact number of interviewees.

All virtual FCR encounters will occur using an application platform that is approved by Information Technology at UC Davis Health System as meeting HIPAA and HITECH data security requirements. The only telehealth communication that will occur will be through the HIPAA-compliant application. No telehealth encounter will be recorded or stored in any way.

Participants will decide to what extent they want to participate in the interviews and surveys. There will be no personal or intrusive questions. In all steps of this pilot study, the risk of loss of confidentiality is very low given the measures described above to protect PHI.

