This study is evaluating a systems-level intervention; a system-level intervention means that we are doing an intervention on how we deliver healthcare. In other words, our intervention is a test of change to the healthcare system. In this case, the system is how we deliver family-centered rounds. The study team will not be able to determine the feasibility and implementation of the pilot project without collecting the implementation data on all patients. It is important that we collect data on all eligible subjects, because we want to ensure that we include gathering data from underserved populations in order to learn how to better provide them with clinical services that meet/address their unique needs. This aspect is particularly relevant for telehealth interventions, whereby the ditigal divide is potentially designing/deliverying telehealth services that do not serve diverse populations. It is therefore important to have all of our diverse groups represented in our data in order to conduct our comprehensive intervention evaluation (Aim 3). We recognize the limitation that our survey-based outcomes (for Aims 1 and 2) will only gather data from those who complete the survey, and thus the conclusions from survey-based data will only be generalizable to similar populations as those represented in those surveys. However, our other outcomes (that rely on FCR observations and review of the EHR, incident reports, and

**PROTOCOL TITLE: Virtual Family-Centered Rounds in the Neonatal Intensive Care Unit:  
A Randomized Clinical Trial**

helpdesk technical issues log) will include all our subjects – and thus represent diverse groups.

Since this is a systems-level intervention, only collecting data on consented patients will provide Aim 3 (intervention evaluation) results that are biased and therefore not useful. We cannot understand how to refine and deliver our telehealth intervention (and thus improve this clinical service line) without having data on all eligible patients. Although we will need to collect data on every patient, the family members in the intervention group can choose if and how much to use the intervention (they can decide to never provide their cell phone number and to never use telehealth for FCR).

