#### **Methods in analysis to handle protocol non-adherence and any statistical methods to handle missing data**

The primary analysis strategy – a modified intention-to-treat analysis – differs from intention-to-treat only in that it will not require replacing missing data with imputed values. This ‘complete-case’ analysis strategy assumes that missingness is at random. Sensitivity analysis using multiple imputation will be performed to assess the potential impacts of nonignorable missingness and alternative approaches for handling infants whose disposition is not to the home

and thus for whom the outcome may not be as applicable. In particular, for the few infants who transfer to another unit or hospital, the parent-reported outcomes and the 30-day revisit/readmission outcomes are of limited applicability. Our modified intention-to-treat analysis will include these subjects, but alternative analysis that excludes such outcomes from infants not discharged to home would be warranted. We will also estimate alternative treatment effects, such as per-protocol and as-treated.

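### The SAP gives multiple imputation the job of assessing nonignorable missingness but specifies no departure from missing at random, so for the parent-reported outcomes that job may go undone

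*Combined protocol and SAP*

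**What the plan says.** The SAP section on protocol non-adherence and missing data describes the primary strategy as a modified intention-to-treat, complete-case analysis, and says that this "analysis strategy assumes that missingness is at random". The next sentence reads "Sensitivity analysis using multiple imputation will be performed to assess the potential impacts of nonignorable missingness", and goes on to give the same sensitivity analysis a second task: alternative handling of infants not discharged home.

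The only other mention of imputation is in protocol section 8 (Data analysis), which promises "sensitivity analyses using multiple imputation approaches for missing data to complement the primary analysis". Neither place gives an imputation model, auxiliary variables, a shift parameter, a pattern-mixture or selection model, a reference-based rule or a tipping-point range. The other analyses listed in that SAP section (excluding infants not discharged home, per-protocol, as-treated) change the population or the estimand. They do not address nonignorable non-response.

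On the amount of missing data, section 8 (Sample size) states: "Parent-reported outcomes assume a survey response rate of 75% (thus n=321 parents". Later in section 8 the protocol accepts that "survey-based outcomes (for Aims 1 and 2) will only gather data from those who complete the survey", and treats this as a limit on generalizability. Section 7 (Data collection) gives the source of the primary outcome as "FCR parent attendance proportion (captured using weekday rounding observations"; length of stay comes from the health record.

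**The concern.** Imputation can speak to nonignorable missingness only if the analyst puts a departure from missing at random into it. The stated purpose requires such a departure and the stated method does not supply one. An analyst following the text could run default imputation, see it agree with the complete-case result, and have learned nothing about nonignorable non-response. Alternatively, a departure could be chosen after the data are seen. Pre-specification should close off both routes.

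The setting makes this more than a formality. About a quarter of the parent-reported data are expected to be missing. These data carry the hypotheses on experience, activation, distress and quality of life, and also 90-day breast milk feeding. Section 7 has a coordinator invite intervention-arm parents to subscribe, whereas contact with control-arm parents is described as a survey invitation. Parents therefore know whether they were offered virtual rounds. Satisfaction and distress are outcomes and also plausible reasons to answer or ignore a survey. If that dependence differs by arm, the between-arm comparison is biased, which is a different problem from limited generalizability.

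**Working it through.** **Inputs from protocol section 8 (Sample size).** 447 randomized (298:149), 4% attrition, 429 evaluable; 80% power, two-sided 5%; log length of stay with SD 1.0; a 25% reduction in the geometric mean; 75% survey response, 321 parents.

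**The plan's own figures reproduce.**
- ln(0.75) = -0.2877. Control n = 1.5 × (1.960 + 0.842)² × 1.0² / 0.2877² = 142.3, rounded up to 143; total 3 × 143 = 429.
- 429 / 0.96 = 446.9, rounded up to 447. Power at 286:143 is 80.2%.
- 429 × 0.75 = 321.75, stated as 321.

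**Detectable difference for survey outcomes.** I assume one respondent per neonate and a 2:1 split of 321, that is 214:107. The standard error in SD units is √(1/107 + 1/214) = 0.1184. The 80%-power difference is 2.8016 × 0.1184 = 0.3317 SD.

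**What a departure does.** Let m be an arm's missing share and δ the mean amount by which its non-respondents differ from their missing-at-random prediction. The arm mean then moves by mδ, and the effect moves by m(int)·δ(int) − m(con)·δ(con). With m = 0.25 in both arms this is 0.25 × (δ(int) − δ(con)). The δ values below are assumptions; the documents give none.

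| Difference in δ (SD) | Shift in effect (SD) | Shift / 0.3317 |
|---|---|---|
| 0.25 | 0.0625 | 19% |
| 0.50 | 0.125 | 38% |
| 0.75 | 0.1875 | 57% |
| 1.00 | 0.25 | 75% |

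**Tipping points for an observed effect of 0.3317 SD** (standard error held at 0.1184):
- Significance is lost at (0.3317 − 1.960 × 0.1184) / 0.25 = 0.40 SD.
- The effect reaches zero at 0.3317 / 0.25 = 1.33 SD.

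**Does ordinary imputation show the problem?** I simulated 600 trials of 286:143 with true effect zero, one covariate and 20 imputations. A quarter of the control arm was missing at random. A quarter of the intervention arm was missing with dependence on the outcome itself (assumed log-odds slope 1 per SD). Mean estimates were:
- complete-case: +0.163 SD
- missing-at-random imputation: +0.162 SD
- imputation with the matching shift of -0.66 SD: -0.003 SD

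The Monte Carlo standard error of the complete-case mean was about 0.004. Imputation without a departure term reproduced the bias; with the matching term, the bias went.

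**The case against.** The strongest reply is that the plan is under-specified and not wrong. A reader might infer that the SAP contradicts itself by using a missing-at-random method for a nonignorable problem. The documents do not support that. They never say the imputation will assume missing at random, section 8 speaks of approaches in the plural, and delta-adjusted imputation is itself multiple imputation. This stands: the defect is an unstated mechanism.

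A reader might also want to say that the planned analysis fails to test the missing-at-random assumption. No analysis of the observed data can test it, including the one recommended here. Only sensitivity to it can be assessed.

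Nor does imputation always just repeat the complete-case analysis. It can use auxiliary variables outside the primary model, such as health-record data, observed attendance and other survey waves. In 600 further null trials of 286:143 at 75% response, with the same slope in the intervention arm and 20 imputations, unadjusted complete-case bias and imputation bias were:
- 0.224 and 0.123 SD with an auxiliary correlated 0.7 with the outcome
- 0.214 and 0.162 SD at correlation 0.5
- 0.208 SD for both with no useful auxiliary

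Good auxiliaries can therefore reduce the bias and make the two analyses disagree. In these runs they did not remove it. The close agreement in the single-covariate simulation owes much to having no separate auxiliary.

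The magnitudes also depend on assumed mechanisms, and the 0.25 multiplier needs equal response in both arms. Both objections are fair. Finally, it would be a prediction about the authors, not something in the documents, to say that agreement between analyses will be reported as robustness.

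**Conclusion.** The point holds as a gap between purpose and specification. The SAP commits to assessing nonignorable missingness and names a tool that does so only with a component found nowhere in the protocol or SAP. Run in its ordinary form, the analysis would not deliver what is claimed for it.

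The reach is the parent-reported secondary outcomes. A reader might infer that the primary conclusion is in doubt. It is not on this ground: attendance is recorded by observation of rounds, and length of stay, which sets the sample size, comes from the health record.

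The shifts in effect are illustrations of what an unexamined departure could do, not estimates of bias in this trial. They rest on the assumed differences in δ, 25% missing in each arm and a 214:107 split. At the middle assumption of 0.50 SD the shift is large enough to take an effect at the detectable size out of significance. The plan should be changed before the survey outcomes are analyzed.

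**What to change.** In the SAP section on missing data:

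1. Label standard multiple imputation as the missing-at-random sensitivity analysis. State its imputation model and auxiliary variables, such as health-record data, observed attendance and scores from other survey waves.
2. Name the key parent-reported outcomes. For these, pre-specify delta-adjusted (pattern-mixture) imputation with shifts set separately by arm: in SD units for continuous scores, and in log-odds for binary outcomes such as top-box items and 90-day breast milk feeding, where an SD shift does not apply.
3. Choose a range wide enough to reach the tipping point, and report that point for each conclusion. A range stopping at 0.5 SD could be too narrow: in the illustration above, an effect at the detectable size reaches zero only at 1.33 SD.
4. If this is not wanted, delete the statement that nonignorable missingness will be assessed.

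The cost is a short SAP addition and repeat runs of the planned imputation with offsets. The work grows with the number of outcomes and with the four survey time points, which is why it should be limited to the key outcomes. It needs no new data and no change to sample size or trial conduct.

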## 2) Objectives

The overall objective of this study is to test the efficacy of virtual family-centered rounds (FCR) compared to standard rounds for NICU patients and to conduct an intervention evaluation of the virtual FCR intervention.

**Aim 1: Evaluate the impact of virtual FCR on parental activation and wellbeing.** The primary outcome will be FCR parent attendance proportion (number of round encounters with a parent present – either virtually or in person – divided by total number of round encounters). Increased parent FCR attendance would increase the delivery of best practice. We will also compare parent experience (Child HCAHPS) and parent activation (P-PAM) at discharge and parent distress and quality of life at 0, 30, 60, and 90 days from discharge between assigned trial arms. Parent wellbeing promotes neonatal wellbeing.

- *Hypothesis1a: The virtual FCR (intervention) group will have a higher parent FCR attendance proportion compared to the standard FCR (control) group.*
- *Hypotheses1b: Parents of virtual FCR neonates will report (a) better experience, (b) higher activation, (c) less distress, and (d) better quality of life compared to parents of standard-of-care neonates.*

**Aim 2: Evaluate the impact of virtual FCR on neonatal outcomes.** We will compare breast milk feeding at discharge and 90 days from discharge, growth failure, medical errors, and NICU length of stay between assigned trial arms.

- *Hypotheses2: Virtual FCR neonates will have (a) greater breast milk feeding, (b) reduced growth failure, (c) fewer errors, and (d) shortened length of stay compared to standard-of-care neonates.*

**Aim 3: Conduct a mixed methods evaluation of the virtual FCR intervention.** We will measure all five RE-AIM dimensions using quantitative (chart review, surveys) and qualitative (observations, interviews) methods. Observations will be of NICU FCR; interviews will be with intervention arm parents and NICU providers. We will use a convergent design and merge data in the analysis and reporting phases.

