**ASSIGNMENT TO CONTROL VERSUS INTERVENTION:** The unit of randomization is at the subject (neonate) level. The study statistician will generate a random allocation list and employ allocation concealment to assign eligible subjects with a 2:1 intervention-to-control arm ratio. During the 12-month enrollment (intervention delivery) period, a research coordinator will open the sequentially numbered assignments to invite parents of neonates assigned to the intervention arm to sign up for virtual FCR. Neonates of parents accepting this offer will be considered “subscribed.” For neonates with more than one eligible parent, separate subscription invitations will be used for each parent.

**DELIVERY OF INTERVENTION:** We will use Extended Care as the software interface for virtual FCR. This secure platform meets HIPAA security rules and launches from the electronic health record. Parents will use the Extended Care application on their personal computer or smart device. The NICU medical team will use Extended Care on a computer on wheels with a speaker and camera. Virtual FCR will be available for parents of subscribed neonates to attend Monday through Friday. For neonates with a subscribed parent, a NICU team member will launch an ExtendedCare telehealth visit (“virtual room”) from the patient’s Epic chart. From ExtendedCare, a NICU team member will use the “invite” feature to invite the subscribed parent(s); the parents then receive a message to their email/cell phone that includes their child’s unique Extended Care link. The parent(s) can use this link, if desired, to enter the “virtual room.” If a parent joins, they will establish the live, bidirectional audio and visual connection. FCR will then proceed in usual fashion. Parents can participate in virtual FCR as much, or as little, as they choose. They can also participate in FCR in person (standard of care) or not participate at all.

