## 18) Provisions to Protect the Privacy Interests of Subjects

All information will be kept in secure REDCap or Excel databases and the only link between the patient and the REDCap will be a Study ID. We will use a "Participant Log" excel file to store data that links the Study ID with the subject. This log will include the following information: Study ID, patient name, MRN, CSN, intervention vs. control arm, admit date, enrolled date, parent identify (e.g., "mom"), parent cell/email preferred contact, subscription status, and disposition. This "Participant Log" will be stored on the secure UC Davis server.

Families will be free to use the intervention if/when it works for them. Families randomized to the intervention can opt out of using it entirely, with no penalty to them or their child. Families are free to answer (or not answer) the surveys the week of discharge and at 30, 60, and 90 days after discharge, with no penalty to them or their child.

Only members of the research team will have access to the data.

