## STATISTICAL ANALYSIS PLAN

### Statistical methods for primary and secondary outcomes

Our primary analysis strategy will analyze all available data from participating family units and their members, with groups defined according to the randomized assignment (intervention versus control) for that family unit. We will use graphical and analytical descriptive statistics to summarize infant, parent, and family unit characteristics. We will use methods for clustered survey data to adjust confidence intervals for family units with multiple parental respondents. We will not use cluster-adjusted confidence intervals for family units with multiple infants unless the mean number of infants per family unit unexpectedly exceeds 1.10.

We will use generalized linear models to estimate intervention effect sizes and confidence intervals and to test hypotheses for outcomes. Independent variables will include a binary indicator for intervention assignment along with a parsimonious set of subject characteristics as covariates (parent age, race, ethnicity, gender, education, transportation security, marital status, other children dependents, digital literacy score). We will specify the generalized linear mixed models as linear, logistic, or Poisson regressions, according to the outcome type. Random effects will be specified to accommodate the multilevel structure of the data and the nesting of longitudinal measurements, when applicable, within parents and the nesting of parents and infants within family units.

To account for increased exposure among subjects with longer neonatal intensive care unit (NICU) stays when analyzing the primary outcome, we will use Poisson regression to compare rates for the family-centered rounds (FCR) parent attendance outcome between intervention vs. control group subjects, using the numerator for this outcome as the dependent variable and using the logarithm of the denominator as an offset term. We will also use Poisson

regression for analyzing the error rate outcomes, with the offset being the logarithm of the number of days in the NICU. The exponentiation of the Poisson regression coefficient for the treatment indicator will thus represent an adjusted between-arm rate ratio for FCR parent attendance.

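### The supplementary per-protocol and as-treated effects sort families by voluntary uptake, so they can show benefit or harm when there is none

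*Combined protocol and SAP*

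**What the plan says.** The main comparison is by randomised arm. The SAP section on statistical methods analyses all available data "with groups defined according to the randomized assignment (intervention versus control) for that family unit". The section on non-adherence and missing data calls this a modified intention-to-treat analysis that "differs from intention-to-treat only in that it will not require replacing missing data with imputed values". That section then closes with: "We will also estimate alternative treatment effects, such as per-protocol and as-treated". It does not say what makes a family treated or adherent, whom they are compared with, which outcomes are analysed this way, or whether any adjustment is made for who takes up the offer.

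Uptake is voluntary at two steps. Under Protocol section 7 (Procedures Involved), intervention-arm parents are invited to sign up, and those who accept are classed as subscribed. After that, "Parents can participate in virtual FCR as much, or as little, as they choose". Section 11 (Withdrawal of Subjects) lets families in the intervention arm leave it unused, so non-use is not a protocol deviation.

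The primary outcome in section 2 (Objectives) is "number of round encounters with a parent present – either virtually or in person – divided by total number of round encounters". The SAP models it by Poisson regression, "using the numerator for this outcome as the dependent variable and using the logarithm of the denominator as an offset term". Section 18 lists what the participant log holds, including "parent cell/email preferred contact, subscription status, and disposition".

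**The concern.** Subscription and use both happen after randomisation and depend on the family. Any contrast that groups families by them mixes the effect of virtual rounds with whatever distinguishes families who take up the offer.

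Two outcomes have a further problem if treated means having joined virtually:

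- **Attendance.** Presence counts "either virtually or in person", so every virtual user has at least one attended round by construction. Exposure is then part of the outcome.
- **Length of stay.** A longer stay gives more rounds, hence more chances to join at least once. Ever-users will tend to have longer stays even if virtual rounds do nothing.

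Because non-use is permitted, per-protocol has no self-evident meaning in this trial, and the definition could be settled after the data are seen. What is at stake is a null as-randomised result reported beside an apparent gain or harm that the SAP calls a treatment effect.

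**Working it through.** **1. The plan's own figure.** Section 8 (Sample Size) gives SD 1.0 on log length of stay, a 25% reduction in geometric mean, 2:1 allocation, two-sided alpha 5%, 80% power and 4% attrition.

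- Log difference: -ln(0.75) = 0.2877.
- Control n = (1.960 + 0.842)² × 1.0² × (1 + 1/2) / 0.2877² = 142.3, rounded up to 143.
- Intervention n = 286; total 429; 429/0.96 = 446.9, so 447.

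The stated 429 and 447 reproduce, and nothing below changes them. The checks use 286 versus 143.

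**2. Arithmetic for a subscription-based definition.** Uptake and the baseline difference between subscribers and non-subscribers are not in the documents. Assume uptake c of 60% or 80%, a true effect of 10 points in subscribers, and a baseline gap g of +10 points (subscribers attend more) or -10 points (subscribers attend less). Relative to the control mean, subscribers start at g(1-c) and non-subscribers at -gc.

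- Intention-to-treat = 10c: 6 or 8 points.
- Per-protocol (subscribers vs control arm) = 10 + g(1-c).
- As-treated (subscribers vs all others) = per-protocol + gc × n₀/(n₀+143), where n₀ = 286(1-c) is 114.4 or 57.2.
- Complier effect = intention-to-treat / c = 10 points.

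| Uptake | Gap g | Per-protocol | As-treated | Complier |
|---|---|---|---|---|
| 60% | +10 | 14 | 16.7 | 10 |
| 80% | +10 | 12 | 14.3 | 10 |
| 60% | -10 | 6 | 3.3 | 10 |
| 80% | -10 | 8 | 5.7 | 10 |

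The complier column stays at the truth. The other two move with the sign of g.

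**3. Simulation with no effect on total attendance.** From the documents: 286 vs 143, and log length of stay with mean 3.0 and SD 1.0. Weekday rounds (5/7 of days) form the denominator. Assumed: mean attendance 0.20, 0.35 or 0.50, varying between families as a beta distribution with concentration 4; about 57-60% subscription; half of subscribers' attended rounds virtual, purely replacing in-person attendance; logit slope of subscription on attendance propensity from -1 to +1 per SD. Each setting had 400 replicates. Ratios are crude; the true ratio is 1.00.

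| Contrast | Frequent attenders subscribe more | Unrelated | Infrequent attenders subscribe more |
|---|---|---|---|
| Subscribers vs control arm | 1.09-1.28 | 0.99-1.00 | 0.68-0.91 |
| Subscribers vs everyone else | 1.15-1.57 | 1.00-1.01 | 0.57-0.86 |
| Ever-virtual vs control arm | 1.11-1.51 | 1.02-1.26 | 0.87-1.08 |
| Ever-virtual vs never-virtual | 1.19-1.97 | 1.04-1.43 | 0.81-1.11 |

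Intention-to-treat was 0.99-1.01 throughout. In the middle column subscription is unrelated to attendance, so the ever-virtual excess there comes from defining use by attending.

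**4. Length of stay, no true effect.** With 60% subscription unrelated to attendance and 1,000 replicates, the geometric mean ratio was 1.28-1.53 for ever vs never users, 1.17-1.38 for ever-users vs the control arm, and 0.99-1.00 for subscribers vs the control arm.

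**5. A secondary outcome with no effect.** If the outcome shifts by an assumed 0.3 SD per SD of attendance propensity, subscribers vs everyone else rejects at 5% in 14-44% of trials when uptake is selective in either direction, and in 4-7% when it is not.

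**The case against.** The strongest reply is that the inference that matters is protected. The primary analysis follows randomised assignment, no decision rule depends on the alternative effects, and they occupy one sentence whose wording leaves room for a complier estimate. All of that stands, and it limits how serious the point is.

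A reader might infer that these analyses would always show benefit. The documents do not support that. Nothing in them says subscribers are the more engaged families. Section 3 (Background) describes parents kept away by distance, travel, work and childcare, so uptake mainly by infrequent attenders is plausible, and the ratios then mostly fall below 1. For length of stay, an ever-used definition points to harm.

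A reader might also infer that the SAP plans to drop or reassign families who do not attend, or to compare users with everyone else. It says neither. The circularity needs two choices the SAP leaves open: treatment defined by virtual use, and application to attendance. It rules out neither.

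Substitution of virtual for in-person attendance is partly addressed elsewhere. The additional-analyses section separates the two types and examines their association within the intervention arm. That does not repair an adherence contrast. The model covariates include transportation security, other dependents and digital literacy, which plausibly drive uptake. However, the SAP does not say they apply here, and the list omits residence-to-NICU distance, illness severity and length of stay.

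A complier analysis also has conditions. That controls cannot subscribe is inferred from section 7, where only intervention-arm parents are invited; it is not stated. The protocol randomises the neonate, whereas the SAP speaks of assignment for the family unit. A control infant's parent might therefore be subscribed through a sibling. The estimate also needs a scale, because the primary model is a Poisson rate ratio.

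**Conclusion.** The concern holds in limited form. As planned, the per-protocol and as-treated effects are undefined and rest on voluntary behaviour after randomisation. They can show benefit or harm when there is none, and the sign cannot be known in advance. With no true effect, attendance ratios ran from 0.57 to 1.97 across definitions and selection patterns, against 0.99-1.01 by randomised arm. Virtual use as the exposure is partly circular for attendance, and ever-use favours longer stays (1.28-1.53).

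These sizes depend on assumed uptake, attendance level, virtual share and selection, none of which the documents give. They show a range, not a forecast. The as-randomised primary analysis and the sample size are unaffected, so this should be corrected but does not threaten the trial's main conclusion.

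**What to change.** - Make the adherence-adjusted estimate a complier average causal effect, with random assignment as instrument and subscription as uptake. State the scale, for example difference in attendance proportion or difference in log length of stay.
- First confirm, and record in the SAP, that control families could not subscribe, including those with a sibling in the other arm.
- Do not use virtual attendance as the exposure for the attendance outcome.
- If any per-protocol or as-treated result is kept, define treated in advance, name the comparator and outcomes, and label it an exploratory association.

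**Cost.** The change is a short SAP edit plus one additional model, and subscription is already logged. The interval is wider than intention-to-treat by about 1/uptake: 1/0.6 = 1.67 at an assumed 60%, 1/0.8 = 1.25 at 80%. For log length of stay, the intention-to-treat 95% half-width is 1.96 × 1.0 × √(1/286 + 1/143) = 0.20. At 60% uptake it becomes about 0.20/0.6 = 0.33. The estimate also assumes that assignment acts only through subscription, which should be stated beside the result.
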